**Abbreviations**

ALK	Anaplastic lymphoma kinase
BMI	Body Mass Index
CI	Confidence Interval
CNN	Convolutional Neural Network CNN
EMT	Epithelial-to-mesenchymal transition
FISH	Fluorescence in situ hybridization
ERK	Extracellular signal-regulated kinase
FFPE	Formalin-Fixed, Paraffin-Embedded
H&E	Hematoxylin and Eosin
IHC	Immunohistochemistry
mTOR	mammalian target of rapamycin
MIL	multiple instance learning
NGS	Next-generation sequencing
NSCLC	Non-small-cell lung cancer
NR	non-responder
SCLC	Small-cell lung cancer
SMC	Sheba Medical Center
VEGFR	Vascular endothelial growth factor receptor
WSI	whole slide image

## 1. Background

About 4% of NSCLC patients harbor a rearrangement of the ALK gene, producing a novel chimeric kinase that drives cancer evolution and progression. ALK inhibitors have been developed and are currently the most active agents for the treatment of such patients, with a response rate around 80% (82.9% for alectinib-treated patients on the ALEX study). Regarding long-term outcome, on the ALEX trial at five-years follow up, the median survival was not reached yet with 62.5% of the alectinib-treated patients still alive. However, a subgroup of these patients do not respond to this treatment or demonstrate only a short-term response followed by rapid progression. Specifically, in the ALEX study, the one-year event-free survival was 68.4% (95% CI 61.0% to 75.9%), meaning 31.6% had progressed or died on alectinib within a year. In the CROWN study, 78% (95% confidence interval [CI], 70 to 84) were alive and without disease progression at 12 months in the lorlatinib group; thus, with this treatment only 22% had progressed or died within the first year. These results are numerically better with lorlatinib vs alectinib. However, the confidence intervals overlap and in general cross-trial comparisons are not valid. Therefore, and especially considering the very good long-term survival data for alectinib, lorlatinib is considered more relevant for later-line treatments.

No tools are currently available to predict the response to ALK inhibitors and to identify the sub-group of patients that will progress rapidly. Mechanisms of resistance are multiple, consisting of pathway-dependent ALK mutations or amplifications, or off-target activation of bypass growth-factor signaling pathways. Additional mechanisms of resistance include epithelial-to-mesenchymal transition (EMT), SCLC transformation, activation of drug-efflux mechanisms; in a large proportion of cases, the mechanism of resistance remains elusive.

Prediction of resistance is limited currently. Variant 3a is recognized as one with higher rate of resistance development, mostly by ALK mutations. In general, resistance to advanced-generation ALK inhibitors is more commonly accompanied by ALK mutations. Importantly, identification of ALK fusion by IHC may be a less reliable method than FISH or NGS.

Considering the poor outcome of some of ALK positive patients on ALK inhibitor treatment, it can be speculated that prediction of poor response to such treatment may allow personalized tailoring of more aggressive therapeutic options that are currently being tested in clinical trials. Such options include combination strategies with chemotherapy (e.g. study NCT05200481), combination with VEGF-signaling inhibition (e.g. NCT04227028), or with mTOR or ERK pathway inhibition.

Artificial intelligence-based methods of picture analysis have recently emerged as a novel way to characterize tumor specimens. The advent of digital pathology in combination with machine learning and other AI tools appears as the next revolution in the field of pathology. AI tools are currently being tested for diagnosis and quantification of specific tumor characteristics such as IHC stains or prediction of specific genetic aberrations. Furthermore, AI allows integration of spatial information about location of specific cells as well as other features not captured by pathologist review. Recent studies including from our center, demonstrated the feasibility of prediction of the response to immunotherapy based on machine learning of digital pathology H&E sections of melanoma and lung cancer. We aim to use this technique in order identify a sub-group of ALK positive patients that might be candidates for more aggressive treatment options.

## 2. Objectives

### Hypothesis:

Identification of ALK-positive patients' subgroup at risk of rapid progression is possible at the time of diagnosis based on analysis of the H&E (Hematoxylin and Eosin) stained images of tumor sections.

**Goal of the study:** to develop an AI-driven pathologic image analysis-based classifier that can identify patients unlikely to significantly benefit from the currently utilized first-line ALK inhibitors (advanced-generation ALK inhibitors). Our goal is a classifier with final ROC-AUC value of 0.75.

**Endpoint of the study:** the development of a classifier of outcome of ALK patients, to identify patients with a high likelihood of progression on 1st-line ALK inh (2nd or 3rd generation inhibitors) within a year.

### 3. Design

This is a retrospective study.

All data have been collected at different time points during the patients' routine visits at the hospital.

- 1) Collection of a retrospective set of ALK positive patients with advanced NSCLC that have received an advanced-generation ALK inhibitor treatment as the first ALK inhibitor (i.e. alectinib, lorlatinib, brigatinib or ceritinib): collection of the clinical data, pathologic data, response to treatment and scans H&E images
- 2) Image analysis of the scanned H&E images, development of a classifier of the data to identify responders vs. non-responders.

### 4. Origin of the data/biological material

Secondary use and analysis of data.

Potential centers that will participate in the study include any Oncology center that can provide H&E images of diagnostic specimens of ALK+ NSCLC patients with clinical follow up of at least a year. It is expected that each center will be able to contribute 10-20 cases, thus to reach a sample size of 200, about 15 centers are required.

**Ethics:** Each participating center is independent and will receive approval of the local IRB.

**Patient data confidentiality:** No identifying information regarding participating patients will leave each of the centers. Participants will be given a study code, the key connecting the code to the patients' identity will be kept at each participating site secured as per local regulations of each site.

[figure not shown]
### 5. Study conduct

- 1) Participating centers will secure an ethics and administrative approval for retrospective collection of clinical data, and provision of a single H&E stained FFPE section. ALK positive patients will be identified from the working database of each center, data will be collected locally, deidentified and collected centrally. Data collected will include demographics (age, sex, smoking status, co-morbidities, BMI), tumor characteristics (histology, ALK testing utilized, specific test results, co-mutations if known, ALK fusion partner and variants, brain metastasis) and treatment (ALK inhibitor utilized, date initiated, dose reductions, treatment breaks, date of documented progression, date of death or last follow-up). We will aim to include only or mostly patients with NGS results available, to allow for robust and valid identification of the ALK-fusion, as well as the variant type and co-mutations, all proven potential confounders. Next, the required H&E slides will be stripped from identifying details, coded. The scanning of pathology slides will be performed; alternatively, the option of sending the image files instead of the slides themselves is available.
- 2) Image analysis and AI development will be carried out at the Sheba Medical Center, in-house development. The clinical data will be analyzed, tagging study samples as belonging to a responder (R), vs. a non-responder (NR). For the purpose of this study, a NR will be defined as a patient that has progressed or died on an ALK inhibitor treatment within the first year of treatment. Considering most patients would be on alectinib as first-line ALK inhibitor, we expect about 32% of the samples to belong to the NR group. A 30-

70 to 40-60 split between two classes is a reasonable split for the development of a classifier.

The study cases will be randomly split to three: a training cohort, a validation cohort and a test cohort. The cohorts will be stratified by the response to treatment (i.e. equal proportion of R vs. NR cases in each cohort). Next, scanned images will be processed and analyzed. Slides analysis would be done using python using the pytorch packages. Further statistical analysis will be done with R statistical programming.

At first the whole slide image (WSI) is divided into thousands of tiles. These are examined by a convolutional neural network (CNN) to extract tile level features. We will be using Resnet, a common deep learning model used for computer vision as the CNN. The CNN will be trained with multiple instance learning (MIL) at the tile level and later the predicted scores will be aggregated for the WSI level. The final model will be conducted on the slides, to distinguish between R vs. NR. The classifier will be developed on the training cohort, modified if required following processing of the validation cohort and finally tested for efficacy on the test cohort. Cross-Validations techniques will also be used.

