## 6. Inclusion criteria

- Patient aged  $\geq 18$  years;
- Patient with an oncologic disease;
- ALK positive patients with advanced NSCLC that have received an advanced-generation ALK inhibitor treatment as the first ALK inhibitor (i.e. alectinib, lorlatinib, brigatinib or ceritinib).
- Clinical follow up of at least one year from initiation of ALK inhibitor (unless disease has progressed prior to this date).

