## 8. Scientific methods and sample size

The statistical method to define a required sample size for an AI-based algorithm development is not clearly defined at this point. Our target sample size ( $n=200$ ) is based on several approaches of calculations. Firstly, based on our experience with similar type of studies. For example, an AI algorithm predicting the response to immunotherapy based on digital pathology was developed based on a set of 76 cases in total. An alternative approach is based on our goal of a classifier with final ROC-AUC value of 0.75 or above with the null hypothesis value to be 0.5. We are aiming for a type 1 error value of 0.05 and for a power of 90%. Approximately 20% of patients are fast progressors (PD within first year of treatment). Total sample size required based on these assumptions is 96 with 16 fast progressors and 80 responders (calculated by MedCalc). Considering our goal to produce a highly robust classifier, and considering the relative lack of

robust manners to calculate sample size, we'll aim for a sample size that is roughly 2-3 times larger than the mentioned numbers, and have set therefore our goal as n=200.

AI-based analysis of images of the training cohort will be conducted using various methods, including machine-learning and deep learning methods. The methods deemed to provide optimal separation between R and NR will be utilized further and validated on the validation cohort and lastly on the test cohort. Training/validation/test sets will be derived from the entire study samples and split about 70:15:15.

Classification of the cases to R and NR in each phase of the study, on each of the three cohorts (training, validation and test) will be examined for dependence on potential confounders by multivariate analysis. Covariates to be considered include: age, sex, BMI, smoking status, time from diagnosis of advanced disease to ALK inhibitor initiation, specific ALK inhibitor used, ALK-fusion of variant 3 or other, co-mutations, histology, method of ALK-fusion analysis, presence of brain metastasis, site of tissue analysis and site of section scanning. Each of these additional clinical/molecular parameters will be utilized if available for more than 70% of the cohort.

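### The non-responder label counts only events on an ALK inhibitor, so documented progression within the year but after stopping all ALK inhibitors is, read literally, tagged R

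*Protocol*

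**What the plan says.** Section 5 (Study conduct) sets the label: "a NR will be defined as a patient that has progressed or died on an ALK inhibitor treatment within the first year of treatment". It describes the step as "tagging study samples as belonging to a responder (R), vs. a non-responder (NR". R has no definition of its own, there is no not-evaluable class, and nothing is said about events after treatment has stopped.

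Other parts of the Protocol word the same outcome differently:

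- Section 2 (Objectives, endpoint) aims to "identify patients with a high likelihood of progression on" first-line ALK inhibitors within a year. Death is not named.
- Section 8 (Scientific methods and sample size) writes "Approximately 20% of patients are fast progressors (PD within first year of treatment". It has no on-treatment condition and no death.
- Section 6 (Inclusion criteria) asks for "Clinical follow up of at least one year from initiation of ALK inhibitor (unless disease has progressed prior to this date". The clock runs from initiation, and the only exception is progression.
- Section 1 (Background) reports for alectinib that "the one-year event-free survival was 68.4" per cent, and restates the complement, 31.6%, as progression or death *on* alectinib. Section 5 expects about 32% NR.

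The treatment data to be collected are listed in Section 5 as "treatment (ALK inhibitor utilized, date initiated, dose reductions, treatment breaks, date of documented progression, date of death or last follow-up". No date or reason for stopping treatment is listed.

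**The concern.** With two classes and only one of them defined, whoever is not NR is R. Eligibility depends on follow-up from initiation, not on time under treatment, so patients who stop early can enter. One who stops all ALK inhibitors for a reason other than progression and then has documented progression within the year is admitted, fails the literal NR definition, and is tagged R. The hypothesis concerns patients at risk of rapid progression, and such a patient has progressed rapidly.

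The label is both the training target and the reference standard for the test AUC. If these patients resemble other early progressors, tagging them R adds noise to training and pulls the measured AUC down. Whoever assigns the tags also lacks a listed field that separates events on treatment from events after it. Treatment breaks are collected, but the Protocol does not say whether progression during a break counts as on treatment.

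**Working it through.** **1. The plan's own figure.** One-year event-free survival is 0.684 (Section 1), so the event share is 1 − 0.684 = 0.316, which rounds to the stated 32%. With N = 200 (Section 8) that is 0.32 × 200 = 64 NR. The figure reproduces as the share with any progression or death within a year.

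**2. Sections 5 and 6 side by side, read literally.**

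| Course in the first year | Admitted by Section 6? | Tag under Section 5 |
|---|---|---|
| Progression on an ALK inhibitor, including after a switch to another one | Yes (exception) | NR |
| All ALK inhibitors stopped, then documented progression | Yes (exception) | R, by complement |
| Death on treatment without documented progression | No | NR by definition, but not admitted |
| All ALK inhibitors stopped, then death without documented progression | No | None: not admitted |
| No event, one year of follow-up | Yes | R |

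The second row is the mislabelled group. The third is a separate conflict: Section 5 counts these deaths as NR, and Section 6 does not admit them.

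**3. Size.** The documents give no rate of early stopping, so two sets of assumptions are shown. Both assume that mislabelled patients score like other NR patients. If c is their share of all cases tagged R, the measured AUC is 0.75(1 − c) + 0.5c = 0.75 − 0.25c.

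*Route A: assume a share of first-year events falls after all ALK inhibitors have stopped* (N = 200, 64 events).

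| Assumed share | Moved to R | NR left (share of 200) | c | Measured AUC | Moved, 30-case test cohort |
|---|---|---|---|---|---|
| 5% | 3.2 | 60.8 (30.4%) | 3.2/139.2 = 0.023 | 0.744 | 0.5 |
| 10% | 6.4 | 57.6 (28.8%) | 6.4/142.4 = 0.045 | 0.739 | 1.0 |
| 20% | 12.8 | 51.2 (25.6%) | 12.8/148.8 = 0.086 | 0.729 | 1.9 |
| 30% | 19.2 | 44.8 (22.4%) | 19.2/155.2 = 0.124 | 0.719 | 2.9 |

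The test cohort is 15% of 200 = 30 (Section 8 split).

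*Route B: assume 5–15% stop without progression, at uniform times in year one, with a later hazard λ of 1 to 3 times the overall one.* The overall hazard is −ln(0.684) = 0.380 per year. The chance of an event in the rest of the year is 1 − (1 − e^(−λ))/λ, which is 0.168, 0.299 and 0.403 for multiples 1, 2 and 3.

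- Low end: 0.05 × 0.168 = 0.84% of patients (about 2 of 200). c = 0.0084/(0.684 + 0.0084) = 0.012, AUC 0.747.
- High end: 0.15 × 0.403 = 6.05% (about 12 of 200). c = 0.0605/(0.684 + 0.0605) = 0.081, AUC 0.730.

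Route B uses an all-event hazard for everyone who stops. It therefore includes deaths that Section 6 does not admit and patients who switch to another ALK inhibitor, and it overstates the literal group for any given stopping rate.

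**4. Against sampling error.** With 10 NR and 20 R in the test cohort, the Hanley–McNeil variance at AUC 0.75 is (0.1875 + 9 × 0.0375 + 19 × 0.0804)/200 = 0.0103, so the standard error is about 0.10. The shift of 0.003 to 0.031 is about a third of that or less. With the same variance method (two-sided 0.05, against AUC 0.5), test-cohort power falls from about 60% to 56% at the 5% share and to 39% at the 30% share. The 60% starting point reflects the size of the test cohort, not the label.

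**The case against.** The best reply is that *on* is loose usage for *after starting*. Section 1 uses the same wording to restate an event-free survival figure, and Section 8 drops the condition. On that reading nobody is mislabelled, and the label already matches the 32%. This is plausible and stands as a reason not to call the plan's intent wrong. It does not rescue the wording, because the label would still need to be stated as time from initiation.

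A second reply is that a target restricted to time on treatment is coherent with Section 2, which speaks of progression on first-line drugs and of benefit from them. Progression after stopping for another reason need not show failure on the drug. That also stands, but it argues for setting such patients aside, not for counting them as responders, and it would need the stop date.

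A third is that the list of data is introduced as what collection will include, so it may not be exhaustive, and Section 3 adds response to treatment. Fair: what can be said is that the date the rule needs is not among the listed fields.

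A reader might infer more than this. Four stronger readings are not supported:

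- That a patient who stops and then dies within the year is tagged R. Without documented progression, Section 6 read literally does not admit that patient.
- That the planning figure is free of any on-treatment wording. Section 1 attaches it in the same sentence.
- That the label is wrong whatever the target of estimation. The second reply shows otherwise.
- That centres will apply the rule differently. Section 5 places tagging with the analysis and AI development, which appears to be central.

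**Conclusion.** The point holds in a limited form. Read literally, Section 5 sends to R an eligible patient who has stopped all ALK inhibitors and then has documented progression within the year. Sections 2, 5, 6 and 8 do not share one definition of the outcome, and Sections 5 and 6 conflict on deaths without progression.

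The size cannot be found from the documents. If *on* was meant loosely, it is zero. Under the assumed ranges above, a true AUC of 0.75 would read about 0.72 to 0.75, with zero to three patients affected among 30 test cases. The downward direction rests on the assumption that the mislabelled patients score like other early progressors. The effect is small beside the sampling error of the test cohort, so this is a minor correction. It is worth making before data collection, since a stop date is harder to recover afterwards.

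**What to change.** - Use one label in Sections 2, 5, 6 and 8: NR is documented progression or death from any cause within 12 months of starting the first ALK inhibitor, whether or not it is still being taken. This matches the event-free survival figure behind the 32%. Define R as no such event with at least 12 months of follow-up.
- Extend the follow-up exception in Section 6 to death.
- Add treatment stop date and reason to the data listed in Section 5.
- Unless the statistical analysis plan already does so, add a sensitivity analysis that sets aside, and does not tag as R, patients whose event came after stopping all ALK inhibitors.

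The cost is a reworded definition carried through four sections, two retrospective data fields and one extra analysis. The downside is that some events after stopping for reasons other than progression will count as NR. The sensitivity analysis shows how much that matters.

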## 6. Inclusion criteria

- Patient aged  $\geq 18$  years;
- Patient with an oncologic disease;
- ALK positive patients with advanced NSCLC that have received an advanced-generation ALK inhibitor treatment as the first ALK inhibitor (i.e. alectinib, lorlatinib, brigatinib or ceritinib).
- Clinical follow up of at least one year from initiation of ALK inhibitor (unless disease has progressed prior to this date).

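### The one-year follow-up waiver in Section 6 covers progression but not death, so some patients whom Section 5 classes as non-responders cannot enter as the text stands

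*Protocol*

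**What the plan says.** Section 6 (Inclusion criteria) requires "Clinical follow up of at least one year from initiation of ALK inhibitor (unless disease has progressed prior to this date". No other exception is named, and the exclusion criteria in Section 7 do not touch the point.

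Section 5 (Study conduct) sets the class label: "a NR will be defined as a patient that has progressed or died on an ALK inhibitor treatment within the first year of treatment". It then states that "we expect about 32% of the samples to belong to the NR group". The source is the alectinib arm described in Section 1, where one-year event-free survival was 68.4%, "meaning 31.6% had progressed or died on alectinib within a year". Section 5 also has the centres collect the dates of ALK inhibitor initiation, documented progression, and death or last follow-up.

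Two other places word the event more narrowly. The endpoint in Section 2 is a classifier "to identify patients with a high likelihood of progression on" first-line treatment within a year. Section 8 speaks of progressive disease in the first year and puts it at roughly 20%.

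Section 4 describes the centres that could take part as those able to supply slides from "ALK+ NSCLC patients with clinical follow up of at least a year", with no exception.

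**The concern.** The entry rule and the class label do not describe the same patients. Section 5 counts death on treatment as an NR event. Section 6 excuses a patient from the full year only for progression. A patient who dies on treatment in month 4 with no progression recorded is NR by definition, yet has less than a year of follow-up and does not meet the exception.

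This matters because about 15 independent centres pick cases locally from their own databases. One centre may treat follow-up to death as complete and another may apply the sentence as written. A patient who is never submitted cannot be recovered at the analysis stage, and the patients in doubt are early deaths, who belong to the class the tool is meant to find.

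The same sentence has a second effect. A patient who started treatment less than a year before data collection cannot yet show a year without an event. Under Section 6 such a patient can enter after progressing, always as NR, and never as a responder. If centres submit such patients, entry depends on outcome.

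**Working it through.** **1. The plan's own figure.** NR share = 1 − one-year event-free survival = 1 − 0.684 = 0.316, which reproduces the stated figure of about 32%. Deaths count as events in that rate. Per 200 patients: 200 × 0.316 = 63.2 NR.

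**2. Side by side.**

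| Patient in year 1 | Section 5 label | Section 6 entry, read literally |
|---|---|---|
| Progressed on treatment, alive or later dead | NR | Eligible (waiver) |
| Died on treatment, no documented progression | NR | Not eligible |
| Followed a full year, no event | Responder | Eligible |
| Started under a year ago, progressed | NR | Eligible (waiver) |
| Started under a year ago, no event yet | Unknown | Not eligible |

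Row 2 is the contradiction. Rows 4 and 5 together are the recent-starter effect.

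**3. Size of row 2.** Let g be the share of NR who die without documented progression. The protocol does not give g; I assume 5 to 20%.

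- NR lost per 200 = 63.2 × g: 3.2 at g = 5%, 12.6 at g = 20%.
- NR share among those eligible = 0.316(1 − g) / [0.316(1 − g) + 0.684]: 0.3002/0.9842 = 30.5% at g = 5%, and 0.2528/0.9368 = 27.0% at g = 20%.

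**4. Precision in the test cohort.** Section 8 allots about 15% to testing: 0.15 × 200 = 30 cases. The Hanley-McNeil standard error (SE) at A = 0.75, with p NR and n responders, is

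SE² = [A(1 − A) + (p − 1)(Q₁ − A²) + (n − 1)(Q₂ − A²)] / (pn),

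where Q₁ = A/(2 − A) = 0.600 and Q₂ = 2A²/(1 + A) = 0.643.

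| Setting | p | n | SE |
|---|---|---|---|
| 31.6% NR | 9.48 | 20.52 | 0.103 |
| g = 5% (30.5%) | 9.15 | 20.85 | 0.105 |
| g = 20% (27.0%) | 8.10 | 21.90 | 0.110 |

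**5. Recent starters.** This step applies only if centres submit them. Assume uniform start dates over a window of Y = 3 to 6 years and a constant event hazard h = −ln(0.684) = 0.380 per year. The average event probability for a patient in the last year of the window is e = 1 − (1 − exp(−h))/h = 0.168.

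- NR share, with the loss in step 3 included = (1 − g)[(Y − 1)0.316 + e] / {(1 − g)[(Y − 1)0.316 + e] + (Y − 1)0.684}: 35.7% at g = 5%, Y = 3, and 29.0% at g = 20%, Y = 6.
- Recent-starter NR per 200 enrolled = 200(1 − g)e divided by the same denominator: 15.0 and 5.6.

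The range 29.0 to 35.7% lies on both sides of 31.6%, so the documents do not fix the net direction.

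**The case against.** The strongest reply is that the context shows what was meant. Section 5 defines NR for this study with death included, takes its expected share from a rate that counts deaths, and collects the date of death. A minimum follow-up normally serves to keep out patients whose one-year status is unknown, and a patient followed to death has a known status. A careful centre may well read it that way. This carries weight on intent and on severity. It does not remove the conflict: the authors wrote an explicit exception and named progression alone, while naming death in the class definition.

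It is also fair to say that the effect is modest. A 30-70 to 40-60 split is called reasonable in Section 5, not required. The calculation in Section 8 needs only 16 fast progressors, far fewer than the 54 to 61 NR per 200 left under the assumed g (200 × 27.0% to 200 × 30.5%). A change in NR share alone does not move an AUC.

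A reader might go further and take Section 4 as a third entry rule with no waiver. All year-1 deaths would then drop out. Section 1 reports that at five years "the median survival was not reached yet with 62.5% of the alectinib-treated patients still alive". With a constant death hazard (assumed), year-1 mortality is 1 − 0.625^(1/5) = 9.0%, or about 18 per 200. If every one of those deaths were NR, the share would be (0.316 − 0.0897)/(1 − 0.0897) = 24.9%. The documents do not support that use. Section 4 is a feasibility sentence about what potential centres can supply. It does not say when follow-up starts, and the entry criteria stand in Sections 6 and 7. For the same reason it cannot be said that the fastest progressors are shut out: Section 6 admits every patient who progressed before one year, including those who then died.

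**Conclusion.** The conflict between Sections 5 and 6 is in the text and needs no calculation: a death on treatment in year 1 without documented progression is NR and, read literally, ineligible. Its size rests on an assumed g. At 5 to 20%, the loss is 3 to 13 of about 63 NR per 200 and the test-cohort SE rises by about 0.001 to 0.006. That is small to moderate, and the number of patients affected cannot be taken from the documents.

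The recent-starter effect is real under the wording of Section 6 but depends on what centres submit. Section 4 is a wording mismatch to align. A reader might infer that the classifier's AUC will be biased; nothing here shows that. What is shown is that case mix may differ between centres and that the NR group may be smaller than planned. Severity: minor to should-fix.

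**What to change.** - **Section 6.** Require that the ALK inhibitor was started at least 12 months before data collection at that centre, for every patient whatever the outcome. Keep the year of follow-up, and waive it if the patient progressed or died on ALK inhibitor treatment before the year was complete.
- **Section 4.** Replace the free-standing follow-up phrase with a reference to Section 6.
- **Sections 2 and 8.** Use the Section 5 event, progression or death. In the same edit, reconcile the 20% in Section 8 with the 32% in Section 5. If only the wording were changed, one event would carry two rates.

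Patients lost in year 1 without an event remain ineligible under this rule, so some dependence of entry on outcome stays. A count of them per centre would make it visible.

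The cost is wording in four sections, using dates that Section 5 already collects. The downside is that a few recent fast progressors (about 6 to 15 per 200 under the assumptions of step 5) become eligible only 12 months after their start, so some centres may take longer to reach their number.
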